#### Name of Investigational Product:

Tonmya®/TNX-102 SL (Cyclobenzaprine HCl Sublingual Tablets)

#### **Name of Active Ingredient:**

Cyclobenzaprine HCl

#### **Title of Study:**

A 40 to 52-Week Open-Label Extension Study to Evaluate TNX-102 SL Taken Daily at Bedtime in Patients with PTSD

Study period (months): 18 Phase of development: 3

Estimated date first patient enrolled: April 2018

Estimated date last patient completed: September 2019

#### **Objectives**

### **Primary:**

The primary objective of the study is to evaluate the long-term safety of TNX-102 SL 5.6 mg taken daily at bedtime over an additional 40 to 52 weeks in patients with PTSD who have participated in a double-blind lead-in P301 or HONOR study. Some patients will have also participated in an initial 12-week open-label extension study (TNX-CY-P303). This will provide at least 52 weeks of TNX-102 SL 5.6 mg exposure data for at least 50 patients.

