#### Methodology:

This is an open-label, extension trial designed to evaluate safety of additional 40 to 52 weeks of TNX-102 SL 5.6 mg taken daily at bedtime for the treatment of PTSD. There are two possible "tracks" patients can use to enroll into this study:

Track A: patients that complete the double-blind lead-in HONOR study and complete *or are active (at the time of study discontinuation) in the* 12-week open-label extension study, P303, and received active drug in the 12-week double-blind lead-in study, P301/HONOR.

Track B: patients that are currently enrolled in the double-blind lead-in P301/HONOR study that has been discontinued due to results of an interim analysis *or are active (at the time of study discontinuation) in the* 12-week open-label extension study, P303, and received placebo in the 12-week double-blind lead-in study, P301/HONOR.

The study will consist of 5 or 6 in-clinic study visits, including Baseline Visit 1 (Day 0, which is anticipated to be the same visit as the last visit of the 12-week open-label extension study P303 for Track A patients), followed by in-clinic visits after 7, 16, 28 and 40 weeks of open-label treatment. Patients who are active in the 12-week double-blind lead-in study (P301/HONOR) at the time of enrollment to P306 will also have a 2-week phone check-in visit. All Track B patients will have 52 weeks of open-label treatment and a Visit 7. For patients enrolled from the discontinued double-blind lead-in study, P301/HONOR, the P306 Baseline Visit will occur in lieu of an early termination visit.

Patient safety parameters recorded at the final visit in the double-blind lead-in HONOR study (which is the baseline visit in the 12-week open-label extension study P303) can also be used as the baseline safety values for the P306 extension study for Track A patients. Patients will attend clinic visits at 7-, 9-, and 12-week intervals as indicated in the study visit schedule. Eligible patients who provide written informed consent will be provided with a supply of TNX-102 SL 2.8 mg tablets sufficient for

dosing until their next scheduled in-clinic study visit. At each clinic visit, patients will return their TNX-102 SL medication and will receive sufficient supplies to last them until the next scheduled visit. Patients will also have the option to have blood drawn for pharmacogenomic testing.

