## 9.1.2. Screening Overview

The first study visit, Visit 1, will be where the study is explained to the prospective study patient, where written informed consent will be obtained and documented, and where protocol-specified study procedures and assessments will be completed.

For patients enrolling into this study from the 12-week open label extension study, P303, the P306 Baseline Visit (Visit 1) date is intended to be the same date as the final visit of the 12-week open label extension study, P303. However, if there are extenuating circumstances, Visit 1 of P306 may occur within fourteen days of their final visit in P303 without repeating baseline assessments. If more than fourteen days elapse between the final visit of P303 and start of the P306 study, medical monitor approval will be required and baseline assessments will need to be repeated.

For patients enrolling directly from the double-blind lead-in study, P301, all Visit 1 assessments will be performed. These patients are also expected to enter the P306 study at the same time as their final P301 visit; however, if there are extenuating circumstances, then Visit 1 of P306 may occur within fourteen days of their final P301 visit.

Once the patient has provided written informed consent to participate and has met all relevant inclusion criteria, this patient is eligible to begin the open-label treatment period, starting at bedtime on the day of enrollment. The patient should be dispensed three bottles of TNX-102 SL tablets, along with dosing and storage instructions. The end-of-study information collected at the final visit of the 12-week open label extension study P303, or the Visit 1 assessments completed as part of this protocol, will be considered the baseline values for Study P306.

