11.2 Exposure and Compliance

The treatment duration will be calculated as (number of days=last dose date — first dose date+1) and summarized. Participants that are lost to follow up or have a missing last dose date will be assigned a last dose date of the day before the last attended clinic visit for analysis purposes.

All pill count shortage (negative pill count) of greater than 4 doses (8 tablets) per 4-week assessment period and/or any between-visit compliance <70% will be considered protocol deviations, and the reason for the pill count discrepancy will be discussed with the participant and documented in the CRF to ensure that any cases of potential abuse or misuse are identified. Participants with more than one significant incidence of negative pill count discrepancy during the double-blind phase of the study will be closely monitored by the investigator.

Exposure in P306 will be measured using the last date of treatment and first date of treatment. Total exposure will be defined as the last date of treatment minus the first date of treatment plus one. The number of participants with total exposure by visit weeks (eg, 0-12 weeks, >=12-24 weeks, >=24-36 weeks, >=36-48 weeks, and >=48 weeks) will be presented. Additionally, exposure days, defined as the total number of tablets taken divided by 2 (and rounded up to the nearest whole number), will be summarized.

Compliance will similarly be summarized across all study visits for each treatment arm. Study drug compliance as a percentage will be defined as the number of pills taken by the participant divided by the total number of pills that the participant was assigned to take multiplied by 100.

For calculating the compliance and exposure days, the following convention will be applied: for periods where drug is issued, but the participant does not return any bottles or tablets, or the participant misses the visit entirely, that period will not contribute to the compliance or exposure calculation unless the bottles are returned at a later visit.

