12.5 Long-Term Exposure

Summary statistics will be presented for duration of exposure (days and weeks) in the long-term analysis period, defined as the [last dose date of TNX-102 SL – first dose date of TNX-102 SL + 1], for TNX-102 SL. Duration of treatment (weeks) will also be summarized as categorical measures (eg, 0-12 weeks, \ge 12 – 24 weeks, \ge 24 – 36 weeks, \ge 36 – 48 weeks, and \ge 48 weeks).

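### The long-term exposure formula in SAP 12.5 counts off-drug time between studies as TNX-102 SL exposure, so a patient short of 52 weeks of treatment can be credited with 52; the example categories also stop at 48 weeks

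*Protocol*

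**What the plan says.** Under the primary objective, the protocol synopsis states: "This will provide at least 52 weeks of TNX-102 SL 5.6 mg exposure data for at least 50 patients". This is the only number of patients that either document attaches to a length of exposure. Protocol 5.1 and 12.3 and SAP 2.1.1 and 5 do not repeat it, and no sample size calculation stands behind it.

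SAP 12.5 plans summary statistics for "duration of exposure (days and weeks) in the long-term analysis period, defined as the [last dose date of TNX-102 SL" minus the first dose date, plus 1. SAP 12.2 makes clear that the first dose may fall in any of the three studies and that the last dose is the one in P306. For patients on placebo in P301, the clock starts at their first active dose in P303 or P306. No rule subtracts time between studies. SAP 12.5 continues: "Duration of treatment (weeks) will also be summarized as categorical measures (eg, 0-12 weeks", with further steps up to 48 weeks or more. SAP 11.2, for P306 alone, ends at the same point: ">=36-48 weeks, and >=48 weeks) will be presented".

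On rollover from P303, Protocol 9.1.2 says "the P306 Baseline Visit (Visit 1) date is intended to be the same date as the final visit" of P303. It also allows that "Visit 1 of P306 may occur within fourteen days of their final visit in P303 without repeating baseline assessments". Beyond that, "If more than fourteen days elapse between the final visit of P303 and start of the P306 study, medical monitor approval will be required", and no upper limit is given. Patients coming directly from P301 also have a 14-day allowance, although the synopsis says that for them "the P306 Baseline Visit will occur in lieu of an early termination visit".

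**The concern.** A first-to-last-dose span equals time on treatment only if treatment is continuous. Here the span joins up to three studies, and the protocol permits an interval between them in which no study drug need be taken. The error runs one way: a gap can lengthen the credited exposure and never shorten it. If the number of patients reaching 52 weeks is read from this span, some who fall short can be counted in.

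The number matters because SAP 12 exists to support the long-term safety profile, and the 52-week count describes how much evidence lies behind that profile. A separate and smaller point is that a report built on the example categories would not show a 52-week count at all.

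**Working it through.** **Inputs.**
- 52 weeks = 52 × 7 = 364 days; 48 weeks = 48 × 7 = 336 days.
- P301 and P303 last 12 weeks = 84 days each (Protocol synopsis, Methodology).
- P306 lasts 40 weeks (Track A) or 52 weeks (Track B) (Protocol 6.1).
- Visits 6 and 7 have windows of ±7 days (Protocol 9.4, 9.5).
- First P306 dose is on the evening of Visit 1 (Protocol 6.1).
- The gap before P306 is 0 days as intended, up to 14 days routinely, and longer after P303 with approval (Protocol 9.1.2).

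**Assumptions.** The last dose in each study is taken the evening before its final visit. No drug is taken in the gap. A completed P301 or P303 counts as 84 days, because visit windows for those studies are not given here. Any gap between P301 and P303 would also enter the span, but its size is not given.

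**The plan's own figures.** 12 + 12 + 40 = 64 weeks reproduces the maximum duration in Protocol 6.1. The 50-patient figure cannot be reproduced, since no retention rate or split by track is stated. Against the enrolment ceiling it is 50/200 = 25%.

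**Step 1: effect of a gap on the 52-week threshold.** Let d be the sum of within-study durations and g the gap. The SAP 12.5 formula credits d + g. A patient with d below 364 is credited with 364 or more when 364 − g ≤ d ≤ 363.
- g = 0: none.
- g = 7: d = 357–363.
- g = 14: d = 350–363 (50.0–51.9 weeks).
- g = 28 (an assumed longer approved gap): d = 336–363 (48.0–51.9 weeks).

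**Step 2: who can fall in that band.** With a final P306 visit on Day v, P306 contributes (v − 1) − 0 + 1 = v days.
- *Track A completer as the synopsis defines it (active drug in P301), with x days in P303:* at least 84 + x + 273 = 357 + x. This is below 364 only if x ≤ 6.
- *Track B completer with p earlier active days:* p + 357 to p + 371. This is below 364 only if p ≤ 6. With p = 0 the first active dose is in P306 and no gap enters.
- *P301-placebo patient who completed P303 and is treated 40 weeks in P306:* nominally 84 + 280 = 364. An in-window Visit 6 (Day 273–287) gives 357–371. With a 14-day gap, 357–363 is credited as 371–377 (53.0–53.9 weeks). Inclusion criterion 1(a) admits this patient. The synopsis track definitions do not place the patient, while SAP 3 labels P303 entrants as Track A.
- *Early terminator, for example 84 + 84 + 190 = 358 days (51.1 weeks):* with a 14-day gap, credited as 372 days (53.1 weeks).

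**Step 3: the categories.** The top category starts at 336 days, so it pools 336–363 (28 day-values) with 364 and above. The completion table in SAP 12.1 is not a substitute. A Track B completer with no earlier active drug and an in-window Visit 7 has 357–371 days, and 7 of those 15 values are below 364. With Appendix 1's Day 365 ± 7 the range is 358–372, and 6 of 15 are below. These are counts of possible days, not expected shares of patients.

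**The case against.** Four arguments stand against giving this much weight.

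*The 52-week row is not excluded.* The categories are introduced by 'eg', and durations in days and weeks are planned, so the count can be produced without new data. This stands, and it is why the row is secondary. A reader might infer that the SAP drops or forbids the 52-week count; its wording does not support that.

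*The 50-patient figure is a forecast.* It appears once, in the synopsis, and no endpoint or decision rule uses it. This also stands. The count is descriptive, and the case for a sound duration measure does not depend on the figure being a target.

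*The gap rarely matters.* Same-day rollover is intended, and Step 2 shows that almost no completer whom the synopsis places on a track can change 52-week status. This stands as a limit on size. It does not justify a formula that credits untreated time when a simple alternative exists.

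*Summing within-study durations still counts missed doses.* SAP 11.2 does not treat compliance of 70% as a deviation. At that level 0.30 × 280 = 84 days of a 40-week course would be undosed yet still counted, far more than a 14-day gap. This is correct, so the new measure must not be described as days actually dosed. The tablet-based exposure days in SAP 11.2 address missed doses, but only for P306, and they do not correct the three-study span.

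**Conclusion.** The concern holds in a limited form. The SAP 12.5 formula credits between-study off-drug time as exposure. Each gap adds its own length to the patient's duration. At the 52-week threshold, a 14-day gap lets 350–363 days of within-study treatment pass as 364 or more; a longer approved gap widens the band, and same-day rollover changes nothing. The effect on the 52-week count is confined mainly to early terminators, patients with long approved gaps, and any P301-placebo patient who completed P303 and is treated for 40 weeks, a group whose track the documents do not settle. For other completers it is nearly nil. The example categories ending at 48 weeks are a lesser matter of presentation.

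A reader might go further and infer that the study will miss the 50-patient figure, or that the figure is already inflated. The documents support neither. They give no retention rate, no distribution of gaps or visit dates, and no number of patients near the boundary. The result rests on the last-dose convention and on no drug being taken during a gap.

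**What to change.** In SAP 12.5, define duration of exposure as the sum, over the studies in which the patient took TNX-102 SL, of last minus first active dose date plus 1 within that study. Use this definition for the whole 12.5 duration table, so that all rows share one clock, and include a row for 52 weeks or more (364 days or more) reported beside the synopsis figure of 50 patients. The calendar-span version may appear as a separate, labelled column. State that the measure removes between-study gaps only and does not remove doses missed within a study.

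SAP 12.2 takes its duration from 12.5, so state there explicitly that its adverse-event intervals and their denominators stay on the calendar span. Otherwise event onset and time at risk would run on different clocks.

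The cost is one small derivation needing study-specific first and last active-dose dates from the three studies that Section 12 already pools, plus one table row. The 52-week count may come out slightly lower than under the span.

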#### Methodology:

This is an open-label, extension trial designed to evaluate safety of additional 40 to 52 weeks of TNX-102 SL 5.6 mg taken daily at bedtime for the treatment of PTSD. There are two possible "tracks" patients can use to enroll into this study:

Track A: patients that complete the double-blind lead-in HONOR study and complete *or are active (at the time of study discontinuation) in the* 12-week open-label extension study, P303, and received active drug in the 12-week double-blind lead-in study, P301/HONOR.

Track B: patients that are currently enrolled in the double-blind lead-in P301/HONOR study that has been discontinued due to results of an interim analysis *or are active (at the time of study discontinuation) in the* 12-week open-label extension study, P303, and received placebo in the 12-week double-blind lead-in study, P301/HONOR.

The study will consist of 5 or 6 in-clinic study visits, including Baseline Visit 1 (Day 0, which is anticipated to be the same visit as the last visit of the 12-week open-label extension study P303 for Track A patients), followed by in-clinic visits after 7, 16, 28 and 40 weeks of open-label treatment. Patients who are active in the 12-week double-blind lead-in study (P301/HONOR) at the time of enrollment to P306 will also have a 2-week phone check-in visit. All Track B patients will have 52 weeks of open-label treatment and a Visit 7. For patients enrolled from the discontinued double-blind lead-in study, P301/HONOR, the P306 Baseline Visit will occur in lieu of an early termination visit.

Patient safety parameters recorded at the final visit in the double-blind lead-in HONOR study (which is the baseline visit in the 12-week open-label extension study P303) can also be used as the baseline safety values for the P306 extension study for Track A patients. Patients will attend clinic visits at 7-, 9-, and 12-week intervals as indicated in the study visit schedule. Eligible patients who provide written informed consent will be provided with a supply of TNX-102 SL 2.8 mg tablets sufficient for

dosing until their next scheduled in-clinic study visit. At each clinic visit, patients will return their TNX-102 SL medication and will receive sufficient supplies to last them until the next scheduled visit. Patients will also have the option to have blood drawn for pharmacogenomic testing.

#### Number of patients (planned):

The study will enroll up to 200 patients.

#### **Inclusion/Exclusion Criteria:**

#### **Inclusion criteria:**

- 1. The patient has either a) completed a double-blind lead-in HONOR study and completed or is active (at the time of study discontinuation) in the 12-week open-label extension study, P303, or b) is currently enrolled in the double-blind lead-in HONOR study that has been discontinued due to results of an interim analysis, and is judged by the investigator as reasonably compliant, with at least 60% compliance with study medication usage (based on drug accountability).
- 2. The patient has provided written informed consent to participate in this extension study. *Note:* Separate written, signed informed consent will be required if the patient is to participate in the optional pharmacogenomic assessment. A decision not to participate in the optional pharmacogenomic testing will not affect the patient's eligibility for the main study.
- 3. The patient met all prior inclusion and exclusion requirements for the double-blind lead-in HONOR study, or the site received medical monitor approval for the patient to remain in the lead-in study after the retrospective discovery of an entry violation that did not pose any threat to the patient's safety or well-being.
- 4. During the course of the lead-in HONOR study or 12-week open-label extension P303 study, the patient has had no intervening medical conditions including pregnancy, clinically significant increase in suicidal ideation (plan or intent) or significant worsening of depression, newly arising clinically significant abnormal laboratory tests, or any clinically significant, uncontrolled, or unstable medical or surgical condition that could affect the patient's ability to participate in the study or potentially compromise the patient's well-being during the study.
- 5. The patient does not require treatment with a potent (strong) cytochrome P450 subtype 3A4 (CYP3A4) inhibitor, or St. John's wort.
- 6. The patient is willing to refrain from use of all other formulations of cyclobenzaprine for the duration of the study.
- 7. The patient is willing to refrain from use of monoamine oxidase inhibitors for the duration of the study.
- 8. Female patients of childbearing potential continue to agree to practice one of the medically acceptable methods of birth control detailed in the lead-in study.

#### **Exclusion Criteria:**

There are no exclusion criteria for this study.

## Investigational product, dosage and mode of administration:

Name: Tonmya®1/TNX-102 SL (cyclobenzaprine HCl sublingual tablets)

Dose, route, frequency: 2 tablets of TNX-102 SL 2.8 mg taken simultaneously and sublingually (under the tongue) each day at bedtime starting on Day 0 for 40 to 52 weeks.

#### **Duration of treatment:**

40 to 52 weeks

#### Reference therapy, dosage and mode of administration: None

#### **Criteria for evaluation:**

The primary objective of the study is to evaluate the safety of bedtime treatment with TNX-102 SL 5.6 mg for an additional 40 to 52 weeks in patients with PTSD who have either completed the double-blind lead-in HONOR study and completed or are active (at the time of study discontinuation) in the 12-week open-label extension study, P303, or were enrolled in the double-blind lead-in HONOR study that has been discontinued due to results of an interim analysis. Safety will be assessed by the monitoring and recording of AEs, clinical laboratory tests, vital signs, the monitoring of suicidality using the Columbia Suicide Rating Scale (C-SSRS) scale, and the monitoring of depressive symptoms using the Beck Depression Inventory (BDI-II). Safety as well as durability of response will also be assessed by the monitoring of PTSD symptoms using the PTSD Checklist-Specific Version (PCL-S) at Visit 5 (Week 28) and Visit 6 (Week 40) in order to monitor for any potential worsening of PTSD symptoms or its symptoms clusters during the final 12-weeks of the study. Patients enrolled under Track B will also have an additional PCL-S evaluated for safety at their Visit 7 (Week 52). Limited efficacy assessments consisting of the CGI-I, SDS, PROMIS Sleep Disturbance and the BDI-II will be collected at each visit. The PCL-S will be used for efficacy assessments at Visits 5 and 6 only.

#### **Statistics**

#### **Analysis Population:**

The Safety Population will comprise all patients who have been exposed to TNX-102 SL.

#### **Safety Analyses:**

Safety data will be summarized as a single treatment group receiving 1 or more doses of TNX-102 SL 5.6 mg. Adverse events will be coded using the same version of the Medical Dictionary for Regulatory Activities (MedDRA) as used for the lead-in HONOR study and will be summarized overall and by preferred term and system organ class (SOC). Adverse events will also be summarized by severity and relationship to study drug. Serious AEs and AEs leading to discontinuation of study drug will also be summarized. Adverse events that are ongoing in the 12-week open-label extension study P303 or the lead-in double blind HONOR study will be transcribed into the eCRF. All other adverse events that are reported after starting TNX-102 SL in this extension study, or that worsen after entry into this extension study, will be considered newly emergent AEs (NEAEs), even if the type of event was previously reported (and resolved) during either the HONOR study or the 12-week open-label extension study.

Actual values and change from baseline for clinical laboratory test results, vital sign measurements, depression status via the BDI-II and PTSD symptom status via the PCL-S, will be summarized at endpoint using descriptive statistics (n, mean, SD, median, minimum, and maximum). The number of

<sup>1 Tonmya is the FDA conditionally accepted proposed proprietary name for TNX-102 SL for the treatment of PTSD.

patients with baseline and treatment-emergent suicidal ideation and/or suicidal behavior or self-injurious behavior, based on the C-SSRS, will be summarized by treatment group.

